22 APPENDIX E - INHIBITORS OF CYP3A

Examples of inhibitors of CYP3A4/5 can be found at the following website: $\frac{\text{http://medicine.iupui.edu/clinpharm/ddis/table.aspx}}{\text{http://www.pharmacologyweekly.com/content/pages/online-drug-therapy-tables}}.$

The list below reflects information obtained from the website on May 6, 2014. Please refer to the ibrutinib prescribing information for all updates at www.imbruvica.com.

Inhibitors of CYP3A4/5

Strong inhibitors:	Moderate inhibitors:
Indinavir	Aprepitant
Nelfinavir	Erythromycin
Ritonavir	Fluconazole
Clarithromycin	Grapefruit juice
Itraconazole	Verapamil
Ketoconazole	Diltiazem
Nefazodone	
Saquinavir	
Suboxone	
Telithromycin	

UTX-IB-301

1 LIST OF ABBREVIATIONS AND DEFINITIONS OF TERMS

Abbreviation	Definition	
AE	adverse event	
ANC	absolute neutrophil count	
ALT	alanine aminotransferase	
AST	aspartate aminotransferase	
CLL	Chronic Lymphocytic Leukemia	
СМН	Cochran-Mantel-Haenszel	
CR	complete response	
СТ	Computerized Axial Tomography	
CTCAE	Common Terminology Criteria for Adverse Events	
°C	degrees Celsius	
DSMB	Data and Safety Monitoring Board	
FDA	Food and Drug Administration	
ICH	International Conference on Harmonization	
IRC	Independent Review Committee	
ITT	intent-to-treat	
IWRS	interactive web response system	
MedDRA	Medical Dictionary for Regulatory Activities	
mg	milligram	
MRI	magnetic resonance imaging	
NCI	National Cancer Institute	
ORR	overall response rate	
OS	overall survival	
PD	progressive disease	
PFS	progression-free survival	
PR	partial response	
PT	MedDRA Preferred Term	
SAE	serious adverse event	
SOC	MedDRA System Organ Class	
TEAE	treatment-emergent adverse event	

[figure not shown]
2 INTRODUCTION

The original statistical analysis plan (SAP) was based on TG Therapeutics Protocol UTX-IB-301, dated September 9, 2014. This SAP, dated December 10, 2020 is based on the revised Protocol UTX-IB-301, dated July 31, 2017. The SAP summarizes key aspects of the study to provide context for statistical methods and presents details of the statistical methods that the sponsor plans to use to address the study aims. The statistical principles applied in the design and planned analyses of this study are consistent with ICH guidelines E9 (Statistical Principles for Clinical Trials).

The SAP may evolve over time, for example, to reflect the requirements of protocol amendments or regulatory requests. However, the final SAP must be finalized, approved by the Sponsor, and placed on file before database is locked. Deviations from the approved plan will be noted in the clinical study report.

3.1 STUDY DESIGN

This study is a fixed-dose, randomized, two-arm Phase 3 trial to assess the efficacy and safety of ublituximab in combination with ibrutinib compared to ibrutinib alone in patients with CLL who have received at least one prior standard treatment regimen and who have at least one high-risk cytogenetic abnormality (17p deletion, 11q deletion, and/or P53 gene mutation).

Following screening, patients meeting the inclusion/exclusion criteria will be randomized in a 1:1 ratio to one of the following treatment regimens:

- Arm A: Ublituximab + ibrutinib
- Arm B: Ibrutinib

Randomization will be stratified according to prior lines of therapy (1 prior vs. 2 or more prior lines of therapy)

All study patients will be evaluated for response after cycles 2, 4, and 6, then every 3 cycles thereafter if patient is on active treatment, or approximately every 3 months thereafter if patient is in follow up. The best clinical response as well as disease progression will be determined by an Independent Review Committee (IRC).

Patients will continue treatment until the occurrence of definitive disease progression, unacceptable toxicity, or withdrawal from the study due to investigator decision or other reasons. Patients who discontinue study treatment for reasons other than disease progression will continue to be followed for progression and/or survival approximately every 3 months.

Upon first assessment scan of the last randomized patient, and site submission of all required efficacy and safety data, the independent DSMB will review the primary and secondary efficacy analyses, and safety data.

3.2 STUDY TREATMENT

Treatment will be administered on an outpatient basis in 4-week (28 day) cycles. Patients randomized to Arm A will receive ublituximab and ibrutinib, while patients randomized to Arm B will receive ibrutinib alone. Treatment cycle of study treatment is summarized in Table 1.

TABLE 1: TREATMENT OVERVIEW BY CYCLE OF STUDY TREATMENT

Cycle 1:

		Arm B		
Ublituximab			Ibrutinib	Ibrutinib
Day 1	Day 2	Day 8 & 15	Daily	Daily
≤150mg	750 mg	900 mg	420 mg	420 mg

Cycles 2 through 6:

Arm	Arm B	
Ublituximab	Ibrutinib	
Day 1 Cycles 2, 3, 4, 5, 6	Daily	Daily
900 mg	420 mg	420 mg

Beyond Cycle 6:

Arm A	Arm B	
Ublituximab	Ibrutinib	Ibrutinib
Day 1 every 3 months thereafter (e.g. cycles 9, 12, etc.)	Daily	Daily
900 mg	420 mg	420 mg

Patients will continue treatment until the occurrence of definitive disease progression, unacceptable toxicity, or withdrawal from the study due to investigator decision or other reasons.

The Schedule of Events is presented in Table 2.

TABLE 2: STUDY ASSESSMENTS AND TREATMENT SCHEDULE

TABLE 2. STUDI AS	Screen					Cycles 2-6 ²					After Cycle 63	n 1 6
Cycle = 28 days	*		Cycle 1 ¹		C2	C3	C4	C5	C6	q3 Cycles (C9, 12, etc.)	End of	
Procedure\Days	-21-0	D1	D24	D8	D15	Day 1		Day 1	study			
Informed consent	X											
Medical history	X											
Rai Staging	X											
ECOG Performance Status	X	X				X	X	X	X	X	X	X
Physical Examination	X	X				X	X	X	X	X	X	X
Vital signs (pulse, BP, temp)	X	X	X	X	X	X	X	Х	X	X	X	X
BM aspirate/biopsy ⁵	X											
12-lead EKG	X											
Tumor evaluation ⁶	X			-	-	f cycles 2, 4 and 6 then after the completion of every 3 cycles every 3 months if in follow up						
Serology: HCV, HBV, CMV ⁷	X											
MRD ⁸						For patients in PR or CR at response assessment intervals beginning at the Cycle 6 response assessment						
Hematology ⁹	X	X	X	X	X	X	X	X	X	X	X	X
Serum Chemistry ⁸	X	X		X	X	X	X	X	X	X	X	X
PT/INR	X					X		X				
Serum Pregnancy Test ¹⁰	X											
Urinalysis	X											
Quantitative Immunoglobulin ¹¹		X			X		X			X		
β_2 -microglobulin	X											
FISH Analysis ¹²	X											
Concomitant Medications	X	X	X	X	X	X	X	X	X	X	X	X
Adverse Event Evaluation ¹⁵	X	X	Х	X	X	X	X	Х	X	X	X	Х
				Tr	eatmen	t Sche	dule					
Ublituximab Dose X16 X X X X X X X X X X X X X X X X X X												

¹ Physical Exam, Vital Signs, ECOG PS, Hematology and Serum Chemistry visit days have +/- 3 day window

² Physical Exam, Vital Signs, ECOG PS, Hematology and Serum Chemistry visit days have +/- 7 day window

³ Physical Exam, Vital Signs, ECOG PS, Hematology and Serum Chemistry visit days have +/- 14 day window

⁴ Day 2 visit only required for patients randomized into Arm A.

⁵ Unilateral bone marrow aspirate and/or biopsy performed at investigator discretion in patients for whom assessment of extent of CLL involvement and bone marrow cellularity is important in determining eligibility. In addition, a post-baseline bone marrow biopsy should be completed to confirm potential CR by radiological assessment.

⁶ Scans for screening should be completed within 30 days prior to Day 1 of Cycle 1. Response tumor evaluations have a +/- 7 day window. Radiology assessment should include CT or MRI imaging of neck, chest, abdomen, and pelvis.

7 Serum virology to include HBsAg, HBc antibody and CMV. If HBcAg, HBc antibody, HCV or CMV is positive, patients must be evaluated for the presence of

DNA/PCR

⁸ Peripheral Blood sample draw (See study manual for all central lab instructions. +/- 7 day window for MRD sample). For patients MRD negative by peripheral blood, a bone marrow sample should be completed to confirm MRD negativity.

⁹ Must be obtained prior to ublituximab administration if on a day of infusion.

 $^{^{10}}$ For women of child bearing potential, completed within 3 days prior to Day 1 of Cycle 1

¹¹ IgA, IgE, IgG, IgM

¹² For del(13q), del(11q), del(17p), and (12)trisomy, IgHV and P53 gene mutation status in peripheral blood. Central FISH analysis can be performed on UTX-IB-301 study or the TGTX-LAB-001 screening protocol.

¹⁵ If clinically significant adverse event or abnormal result is observed that is not resolved by the end-of treatment visit, continue to monitor and record until stabilization or resolution of event

¹⁶ Patients should receive up to 150 mg on Day 1 and 750 mg on Day 2. Collect a hematology panel prior to Day 2/Cycle 1 infusion.

Ibrutinib Dose	Days 1 – 28 (Daily)	
*Randomize Days -7 to 0		
3.4 STUDY OBJECTIVES		
3.4.1 PRIMARY OBJECTIVE		
	aluate the effect of the addition of ublituximab to ibrutinib on an verall response rate (ORR = $CR + PR$) in patients with previously sk cytogenetics.	
3.4.2 SECONDARY OBJECTI	VES	
The secondary objectives are respect to:	to evaluate the effect of the addition of ublituximab to ibrutin	ib with
 Complete response (C Duration of response Time to Treatment Re Achievement of minin Progression-free Surv Safety profile 	(DOR) sponse (TTR) num residual disease (MRD) negativity	
3.5 POWER AND SAMPL	E SIZE CONSIDERATIONS	
3.5.1 OVERALL RESPONSE	RATE	

The ORR study analysis will be performed when all ITT patients have the opportunity to complete efficacy, safety, and other assessments through at least 16 weeks of evaluation (first planned efficacy evaluation, allowing for a second evaluation to confirm a potential response at first assessment).

3.6 RANDOMIZATION

In this open label study, approximately 120 patients will be centrally randomized in a 1:1 fashion to one of the two treatment regimens. Investigators will use an interactive web response system (IWRS) which will assign patients to either treatment Arm A (ublituximab plus ibrutinib) or treatment Arm B (ibrutinib alone). Randomization will be stratified by prior lines of therapy (1 prior vs. 2 or more prior lines of therapy).

3.7 ANALYSIS POPULATIONS

The Intent-to-Treat (ITT) population will include all randomized patients. The Treated Population will include all patients who received at least one dose of study medication. The Treated Population will be the same as the Safety Population.

Any ITT patient who meets any of the following criteria below will not be included in the Per Protocol analysis:

- Patients who do not meet the following required eligibility criteria:
 - o Diagnosis of CLL which is confirmed as high-risk per the protocol requirement
 - Does not have measurable nodal disease
 - o Has been previously treated with ibrutinib or a BTK inhibitor
 - Does not have a baseline or have at least one on-study post baseline efficacy evaluation by the independent radiology committee

4 GENERAL CONVENTIONS

Descriptive and inferential statistics will be used to summarize results of the study. Standard descriptive statistics, such as mean, standard deviation, quartiles, minimum, and maximum, will be calculated for continuous variables. For discrete variables, descriptive analyses will be based on numbers of patients and related percentages.

All tabular presentations will display two columns of results, one for each of the two treatment regimens. Throughout this analysis plan, the phrase "by treatment regimen" will be understood to mean the two groups described in the previous sentence.

In addition to tabular summaries, all relevant eCRF data will be summarized by patient listings.

4.1 DEFINITION OF BASELINE

In general, the last observed measurement prior to or on the first administration of study treatment will be considered the baseline measurement.

4.2 DEFINITION OF TIME

For the purpose of summarizing/analyzing efficacy data, time will be defined relative to the date of randomization. Unless otherwise stated, for visits (or events) that occur on or after the date of randomization, time is calculated as:

• time (days) = visit date (event date) – randomization + 1 For visits (or events) that occur prior to randomization, time is calculated as: • time (days) = visit date (event date) - randomization date

For listings (such as for adverse events) of the quantity 'days since first/last dose' is defined as:

• days since first/last dose = event date - date of first/last dose

Events that occur on the same day as the first/last dose will therefore be described as occurring zero days from the first/last dose. In most cases, listings will include the number of days since first/last dose of ublituximab/ibrutinib or ibrutinib; however, some listings may present the number of days since first/last dose of study treatment, which is a combination of two agents, or the dose of ibrutinib alone. Labels and footnotes in the data presentations will specify clearly which reference date and therapeutic agent are used.

4.3 MISSING AND PARTIAL DATA

In general, other than for partial dates, missing data will not be imputed and will be treated as missing. The algorithms for imputation of partial dates vary depending upon the parameter and are presented in Appendix A – Imputation Rules for Missing Data.

4.4 SOFTWARE

Unless otherwise stated, all analyses will be conducted using SAS Version 9.2 or higher or other validated software.

4.5 CHANGES TO PLANNED ANALYSES

The Clinical Study Report will document any changes to the SAP made after data base is locked.

5 STUDY POPULATION SUMMARIES

5.1 DISPOSITION

The number and percentage of patients who are included in ITT, Treated Population, Per Protocol populations and the number and percentage of patients withdraw from the study early will be presented by treatment regimen. For randomized patients who withdraw early, the number and percentage withdrawing by withdrawal reason will be presented.

5.2 DEMOGRAPHIC AND BASELINE CHARACTERISTICS

A summary of demographics and baseline characteristics will be presented by treatment arm for the ITT and Treated Population.

The demographic characteristics consist of age, age category (defined below), sex, ethnicity, race, and Eastern Cooperative Oncology Group (ECOG) performance status. Baseline height and weight will also be presented using standard descriptive statistics.

Age (years) will be calculated as (date of informed consent – date of birth) / 365.25.

Age categories, < 65 years and 65 years or older, will be presented using frequencies and percentages.

The number and percentage of patients' ethnicity, race category, cytogenetics category will also be summarized.

5.3 MEDICAL HISTORY

A data listing will present medical history. If useful for interpretation of the results of the study, a table will summarize the data.

5.4 HISTORY OF CHRONIC LYMPHOCYTIC LEUKEMIA

Tables will present information regarding the patients' history of Chronic Lymphocytic Leukemia, including time since initial diagnosis to randomization, primary diagnosis, patient status (relapsed only, or relapsed and refractory), as well as the screening results of the disease assessments and prior lines of therapy.

5.5 PRIOR TREATMENT FOR CHRONIC LYMPHOCYTIC LEUKEMIA

Use of prior treatment for CLL will be presented as frequency counts and percentages.

Prior chemotherapy will be coded using the World Health Organization (WHO) and MedDRA dictionary and summarized by treatment arms for the safety population.

By WHO Drug base substance preferred name using frequency counts and percentages.

By regimen number using frequency counts and percentages on unique combinations of WHO Drug base substance preferred names.

5.6 PRIOR AND CONCOMITANT MEDICATIONS

All medications recorded on the CRFs will be coded using the WHO or MedDRA dictionary. Prior and concomitant medications will be summarized by treatment arm in the ITT and Treated Population by anatomical therapeutic chemical (ATC) Class Level 4 and WHO Drug base substance preferred name.

Prior medications are defined as medications with stop dates occurring before the date of first administration of any study treatment component. Concomitant medications are defined as medications with start dates occurring on or after the date of first administration of any study treatment component and no more than 30 days after the last administration of any study treatment component. Medications with start and stop dates that bracket the date of first administration of any study treatment component will be summarized as both prior and concomitant medications.

For the purpose of summarizing prior and concomitant medications, incomplete medication start and stop dates will be imputed as detailed in Appendix A. Based on imputed start and stop dates, medications that clearly stopped prior to date of first administration of any study treatment component will be included in the prior medications table, and medications that clearly started on or after date of first administration of any study treatment component will be included in the concomitant medications table. All other medications will be included in both the prior and concomitant medications tables.

5.7 STUDY TREATMENT EXPOSURE

The following will be summarized by treatment arm for each of the two study treatment components using descriptive statistics:

- Number and percentage of patients who received at least one dose (Treated Population analysis)
- Duration of exposure, calculated as (date of last dose date of first dose + 1) (for subjects who are continuing on treatment at the time of data cutoff, the duration will be data cutoff date date of first dose +1)
- Number of doses received
- Cumulative dose received

A data listing of reasons for early treatment discontinuation will be summarized (including sites number, patient number, dates of first and last dose administered and last date of contact or visit)

6 EFFICACY ANALYSES

All efficacy analyses will be performed on the ITT population and Treated Population. Measures of tumor response (i.e., ORR, CR rate, DOR, TTR and PFS) will be determined by an Independent Review Committee (IRC).

6.1 PRIMARY EFFICACY OUTCOME

6.1.1 PRIMARY OBJECTIVE: OVERALL RESPONSE RATE

ORR is defined as the proportion of patients with a best overall response of partial response (PR) or complete response (CR). Patients who do not have a tumor response assessment for any reason will be considered non-responders and will be included in the denominator when calculating the ORR. For the ITT analysis, for each treatment group, the number of patients achieving a response will be divided by the total of patients in the ITT population to yield the proportion responding.

The primary efficacy variable (i.e. ORR) will be analyzed in the ITT population first and then will also be analyzed for the Treated Population.

The ORR will be compared between treatment groups by the CMH Test controlling for the randomization strata. Testing of ORR will be at the 5%, 2-sided statistical significance level.

ORR will also be analyzed based on Per Protocol patients. Additional sensitivity analyses will also be performed as appropriate.

6.1.2 SECONDARY OBJECTIVES

6.1.2.1 COMPLETE RESPONSE RATE

The CR rate is defined as the proportion of patients with a best overall response of complete response (CR). Patients who do not have a tumor response assessment for any reason will be considered non-responders and will be included in the denominator when calculating the CR rate. For each treatment group, the number of patients achieving a CR will be divided by the total of patients in the Treated Population to yield the proportion responding.

The CR rate will be compared between treatment groups at the 5%, two-sided statistical significance level using the same methodology described in Section 6.1.1.

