Treatment Study	Ublituximab		Ibrutinib	Ibrutinib	
	Day 1 Cycles 2, 3, 4, 5, 6	-	Daily	Daily	
Visits	900 mg		420 mg	420 mg	
	Beyond Cycle 6:	n A		Arm B	
	Ublituximab		Ibrutinib	Ibrutinib	
	every 3 months thereafter	Daily			
	900 mg	420 mg			
Study Drugs	Ublituximab is a recombinant chimeric monoclonal antibody against the CD20 antigen, available as a 10 mg/mL or 25 mg/mL concentrate for solution for infusion, supplied by TG Therapeutics, Inc. Ibrutinib (Imbruvica®) is a small molecule inhibitor of BTK, available in 140 mg capsules supplied by Pharmacyclics, Inc. / Janssen, Inc.				
	Sample Size:				
Statistical Considerations	Analysis Populations: The intent-to-treat (ITT) p The "Treated Population" w at least one dose of study m	rill includ	e all randomized p	atients who received	

UTX-IB-301 Dated: 31 July 2017 (Ver. 2.5) performed on the ITT and Treated Population. The secondary efficacy analysis and safety analysis will be performed on the Treated Population according to the actual treatment regimen received.

Efficacy Analyses:

Demographic (e.g., gender, age, race, ethnicity) and baseline characteristics (e.g., performance status, height, weight, and prior therapy) will be summarized with descriptive statistics.

For each part of the study, ORR, as determined by the IRC, will be compared between treatment groups by a Cochran-Mantel-Haenzel test with adjustment for the randomization stratification factors.

The CR and MRD negativity rates will be compared between treatment groups using the same methodology as in the analysis of ORR.

Safety Analyses:

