6.1.2.2 DURATION OF RESPONSE

The Duration of Response (DOR) is defined as the interval from the first documentation of CR or PR to the earlier of the first documentation of disease progression or death from any cause.

The DOR rate will be compared between treatment groups at the 5%, two-sided statistical significance level using stratified log-rank test. The median DOR will be estimated by Kaplan-Meier method, The hazard ratio (HR) with 2-sided 95% confidence interval will be estimated using stratified Cox regression model. The DOR analysis will be performed for responders only (CR/PR) in the ITT population.

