6.1.2.4 MINIMAL RESIDUAL DISEASE NEGATIVITY RATE

MRD negativity rate is defined as the proportion of patients in the Treated Population who are MRD negative, excluding any patients who remain on study treatment at the time of the analysis and have a Cycle 1/Day 1 start date less than 6 months from the time of the analyses. For the sake of clarity, the MRD negative analysis will exclude those patients that are too early to evaluate because MRD negativity is only tested for patients on study \geq 6 months. Patients who drop off study for any reason prior to their 6 month visit and do not have an MRD assessment will be included in the analysis and considered non-responders.

For each treatment group, the number of patients achieving MRD negativity will be divided by the total number of eligible patients (see above paragraph) to yield the proportion responding. The MRD negativity rate will be compared between treatment groups at the 5%, two-sided statistical significance level using the same methodology described in Section 6.1.1.

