6.2 ANALYSIS METHODS: DOR AND PFS

The date of definitive progression will be the timepoint at which progression is first identified and confirmed by the independent radiographic committee. Death following the discontinuation of study drug will be considered as an event for the DOR and PFS calculation. Data will be censored on the date of the last tumor assessment (including assessments with a Not Evaluable (NE) outcome) for patients who:

- Start alternative anti-tumor therapy prior to disease progression
- Do not have disease progression within 30 days after discontinuation of study drug(s)

TG Therapeutics, Inc. UTX-IB-301 SAP

secondary outcomes will be tested:

If the primary efficacy analysis of ORR is statistically significant for the ITT population, the following

- Complete response rate
- Duration of response
- · Time to response

For each of these outcomes, ublituximab + ibrutinib will be compared to ibrutinib. The Hochberg approach will be used to control the type I error rate. The null hypotheses state that the secondary outcomes do not differ between ublituximab + ibrutinib and ibrutinib. The three p-values associated with these three secondary outcomes are denoted p_1 , p_2 , and p_3 . The ordered p-values, from largest to smallest, are denoted $p_{(1)} \ge p_{(2)} \ge p_{(3)}$. Specifically:

- If $p_{(1)}$ is less than 0.05, all three null hypotheses will be rejected.
- Otherwise, if $p_{(2)}$ is less than 0.025, the null hypotheses associated with $p_{(2)}$ and $p_{(3)}$ will be rejected.
- Otherwise, if $p_{(3)}$ is less than 0.0167, the null hypothesis associated with $p_{(3)}$ will be rejected.

If the primary efficacy analysis of ORR is not statistically significant, the secondary efficacy variable defined above will not be formally conducted.

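### The plan does not fix which population and grouping supply the complete response (CR) and time to response (TTR) p-values for the Hochberg step, and its stated CR denominator is treated patients rather than ITT as randomised

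*SAP*

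**What the plan says.** **Order of testing.** The multiplicity text (SAP 6.5 in the table of contents, printed after 6.2 in the public copy) opens: "If the primary efficacy analysis of ORR is statistically significant for the ITT population, the following". It then lists CR rate, DOR and TTR and applies Hochberg to one p-value for each. MRD negativity is not on the list.

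**CR rate.** SAP 6.1.2.1 states that "the number of patients achieving a CR will be divided by the total of patients in the Treated Population". It adds: "The CR rate will be compared between treatment groups at the 5%, two-sided statistical significance level using the same methodology described in Section 6.1.1". Protocol 11.10.2.1.1 uses the same denominator.

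**All efficacy endpoints.** SAP section 6 states: "All efficacy analyses will be performed on the ITT population and Treated Population".

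**The other two members of the family.** For DOR, SAP 6.1.2.2 says: "The DOR analysis will be performed for responders only (CR/PR) in the ITT population". For TTR, SAP 6.1.2.3 gives a start date and a censoring rule but no population.

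**Grouping.** The protocol synopsis, under Statistical Considerations, says: "The secondary efficacy analysis and safety analysis will be performed on the Treated Population according to the actual treatment regimen received". Protocol 11.2 assigns secondary efficacy to the Treated Population without a grouping rule. SAP section 7 uses as-received grouping for safety variables.

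**MRD.** SAP 6.1.2.4: "MRD negativity rate is defined as the proportion of patients in the Treated Population who are MRD negative". Patients still on treatment less than 6 months after Cycle 1 Day 1 are left out as too early to test, and the comparison is made at 5% two-sided.

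**The concern.** Hochberg controls error over three specified p-values. Here CR has two candidates, ITT and Treated, and the Treated one could be formed by randomised arm or by regimen received. TTR has the same ambiguity through SAP section 6. For ORR the SAP gives an order, ITT first and then Treated; for CR and TTR it gives none. The choice could then be made after both results are known.

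The denominator that the plan does state for CR is also the weaker one. SAP 3.6 describes the trial as open label. Protocol 6.2 has the site receive the assignment before dispensing and allows up to 7 days from randomisation to first dose. A patient can therefore leave knowing the arm but before any dose, and so drop out of the Treated Population. Protocol 8.5 has ibrutinib, the whole of Arm B, prescribed from commercial supply, so a loss related to arm is plausible, though the documents do not quantify it. As-received grouping adds a second route: an Arm A patient who takes ibrutinib but never ublituximab could be counted with Arm B.

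At stake is whether a CR or TTR claim made under type I error control rests on a pre-specified randomised comparison.

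**Working it through.** **1. The plan's own figures.** The Hochberg thresholds are 0.05/k: 0.05/1 = 0.05, 0.05/2 = 0.025, 0.05/3 = 0.0167. They match the SAP. The planned 120 patients cannot be re-derived, because the available text shows no response rates or power; that is not treated as a defect.

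**2. What each place fixes for the Hochberg inputs.**

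| Endpoint | Own section | SAP section 6 | Protocol synopsis |
|---|---|---|---|
| CR rate | Treated | ITT and Treated | Treated, as received |
| DOR | ITT responders | ITT and Treated | Treated, as received |
| TTR | none named | ITT and Treated | Treated, as received |

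DOR is settled by the explicit sentence in its own section. CR and TTR are not settled.

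**3. Size of the effect on CR.** Inputs from the documents: about 120 patients, 1:1, so 60 per arm; a two-sided 5% test; the SAP's Cochran-Mantel-Haenszel method. Assumed, because the documents do not give them: the CR counts and the numbers untreated or switched. The calculation uses a single stratum, since stratum sizes are not given.

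With a CRs among n in Arm A, b among m in Arm B, N = n + m and k = a + b:

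E = nk/N, V = nmk(N − k) / [N²(N − 1)], X² = (a − E)²/V on 1 df.

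As randomised, 10/60 v 3/60: E = 60 × 13/120 = 6.5; V = 60 × 60 × 13 × 107/(120² × 119) = 2.922; X² = 3.5²/2.922 = 4.19; p = 0.041.

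The same formula gives:

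| Scenario | Table | X² | p |
|---|---|---|---|
| ITT as randomised | 10/60 v 3/60 | 4.19 | 0.041 |
| 3 untreated, all Arm B | 10/60 v 3/57 | 3.82 | 0.051 |
| 1 untreated in A, 3 in B | 10/59 v 3/57 | 3.94 | 0.047 |
| 3 untreated in each arm | 10/57 v 3/57 | 4.22 | 0.040 |
| 3 untreated, all Arm A | 10/57 v 3/60 | 4.62 | 0.032 |
| One Arm A non-responder counted in B | 10/59 v 3/61 | 4.46 | 0.035 |
| One Arm A CR counted in B | 9/59 v 4/61 | 2.33 | 0.127 |

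Excluding a few untreated patients moves p modestly, in either direction according to which arm loses them. Regrouping a single responder moves it more.

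**4. Near the lowest threshold.** With assumed counts of 12/60 v 3/60, p = 0.013. With one untreated in A and five in B (12/59 v 3/55), p = 0.019. These fall on either side of 0.0167, which applies when CR has the smallest p-value and neither earlier Hochberg step rejects.

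**5. No departures.** If every patient is dosed as assigned, the Treated and ITT tables are identical and so are the p-values.

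**The case against.** The strongest reply is that an ITT analysis of CR and TTR is already planned, because SAP section 6 covers every efficacy endpoint in both populations. The Treated Population consists of randomised patients with at least one dose, CR counts unassessed patients as non-responders, and first dose is due within 4 days of randomisation (at most 7), so few should be missing. As-received grouping for efficacy appears only in the synopsis; the later SAP uses it for safety. All of this stands, and it limits the likely size. It does not say which p-value enters Hochberg.

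The illustration is also open to challenge. The counts are assumed and sit near the boundary. Balanced losses leave p almost unchanged, and an uncorrected Pearson chi-square for 10/60 v 3/57 gives 0.0498, which does not cross 0.05. Losing Arm B patients in that example makes significance harder to reach, so it is not evidence of a false-positive risk. The example shows sensitivity, not direction.

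Two stronger readings are tempting. One is that the secondary comparisons are not randomised comparisons at all. The documents do not support that: Treated may equal ITT, and an ITT analysis is planned. The other is that MRD negativity also sits behind the ITT ORR test. It does not; it is outside the Hochberg list and is simply tested at 5%.

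DOR among ITT responders is also conditional on a post-randomisation outcome. That is a separate matter, and changing the population for CR and TTR does not alter it.

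**Conclusion.** The concern holds in a limited form. The SAP specifies a procedure over three p-values but leaves two of them, CR and TTR, without a single defined population. The CR denominator it does state, together with the synopsis grouping rule, is not guaranteed to preserve randomisation in an open-label trial.

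The size is unknown. It is zero if all patients are dosed as assigned. Under the assumed 10 v 3 CRs, three untreated patients move p from 0.041 to between 0.032 and 0.051 depending on arm, and one regrouped Arm A responder moves it to 0.127. These figures rest on assumed counts and an unstratified calculation. The finding concerns secondary endpoints and leaves the primary ITT ORR test untouched. It should be corrected before database lock.

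**What to change.** - **SAP 6.1.2.1, 6.1.2.3 and 6.5:** state that the CR and TTR p-values entering Hochberg come from the ITT population analysed as randomised. For CR, unassessed patients remain non-responders. For TTR, keep the existing censoring of patients who never respond. DOR stays in ITT responders, as already written.
- **SAP section 6:** keep the Treated Population analyses and label them supportive.
- **Protocol synopsis:** limit as-received grouping to safety, in line with SAP section 7. Align protocol 11.2 and 11.10.2.1.1 with the SAP.
- **MRD (SAP 6.1.2.4):** group by randomised arm and keep the rule for patients too early to test, so that they are not counted as failures. Do not add MRD to the three-test Hochberg family, whose thresholds are set for three tests. Label it as outside the type I error control.

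The cost is SAP and protocol wording, with no new data. CR rates may be slightly lower, because untreated patients enter the denominator as non-responders.
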